9.2. Analysis Sets

- Enrolled: Subjects who sign informed consent and are assigned a subject identification number.
- Full: Subjects in the enrolled analysis set who receive a randomized treatment group assignment (rimegepant or placebo) from RTSM.
- DBT safety: Subjects in the enrolled analysis set who take ≥ 1 dose of double-blind study drug (rimegepant or placebo).
- Open-label rimegepant safety: Subjects in the enrolled analysis set who take ≥ 1 dose of open-label rimegepant.
- Double-blind or open-label rimegepant safety: Subjects in the enrolled analysis set who take ≥ 1 dose of double-blind or open-label rimegepant.
- DBT efficacy: Subjects in the full analysis set who are randomized only once and take ≥ 1 dose of double-blind study drug.
- DBT migraine: Subjects in the DBT efficacy analysis set with ≥ 14 days of eDiary efficacy data (not necessarily consecutive) in both the Observation Phase and ≥ 1 month (4-week interval) in the DBT Phase.

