## 4 ANALYSIS SETS, TREATMENT GROUPS, AND SUBGROUPS

### 4.1 Analysis Sets

The following analysis sets are evaluated and used for presentation and analysis of the data:

- Enrolled: Subjects who sign an informed consent form and are assigned a subject identification number, i.e., nonmissing informed consent date. This analysis set is used mainly to assess study population and in by-subject listings.
- Full: Subjects in the enrolled analysis set who receive a randomized treatment assignment from the RTSM system, i.e., nonmissing RTSM randomization date. This analysis set is used mainly to assess study population.
- Safety: subjects in the enrolled analysis set who take  $\geq 1$  dose of study drug (DB rimegepant, OL rimegepant, or placebo), i.e., nonmissing study drug start date. This analysis set is used to assess study population and produce select by-subject listings.
  - DBT safety: subjects in the safety analysis set who take  $\geq 1$  dose of DB study drug (rimegepant or placebo), i.e., nonmissing DB study drug start date. This analysis set is used to assess study population, exposure, and on-DBT safety.
  - OL rimegepant safety: subjects in the safety analysis set who take  $\geq 1$  dose of OL rimegepant, i.e., nonmissing OL rimegepant start date. This analysis set is used to assess study population, exposure, and on-OL rimegepant safety.
    - Interim safety: subjects in the OL rimegepant safety analysis set with OL rimegepant start date – DB study drug last date  $> 7$  days. This analysis set is used to assess post-DBT pre-OL rimegepant safety.
  - DB or OL rimegepant safety: subjects in the safety analysis set who take  $\geq 1$  dose of DB or OL rimegepant, i.e., nonmissing DB or OL rimegepant start date. This analysis set is used to assess study population, exposure, and on-DB or OL rimegepant safety.
  - Follow-up safety: subjects in the safety analysis set whose last contact date is in the follow-up safety analysis period. This analysis set is used to assess follow-up safety.
- DBT efficacy: subjects in the full analysis set who are randomized only once and take  $\geq 1$  dose of DB study drug (rimegepant or placebo). This analysis set is used to analyze outcomes research during the DBT and OLE Phases.

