## 4.2 Treatment Groups

Treatment groups in the DBT Phase are rimegepant 75 mg EOD and placebo EOD. The safety analysis sets are assessed by as-treated treatment group (i.e., actual treatment received), the randomized, full, efficacy, and migraine analysis sets are assessed by as-randomized treatment group, and the enrolled analysis set is assessed overall.

If a subject takes  $\geq 1$  dose of planned randomized study drug, then that subject is considered to have as-treated treatment group equal to as-randomized treatment group (see Section 6.2.6.2).

If there are non-randomized subjects who take study drug, then the as-randomized treatment group of “not randomized” is included in the full analysis set augmented with the safety analysis set.

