### **DB or OL Rimegepant Exposure**

The table of DB or OL rimegepant exposure is provided by treatment group and overall for the DB or OL rimegepant safety analysis set, and summarizes the following parameters descriptively as continuous or categorical variables:

- Time on DB or OL rimegepant (weeks), derived as  $(\text{DB or OL rimegepant end date} - \text{DB or OL rimegepant start date} + 1) / 7$
- Time on DB or OL rimegepant (weeks) categories: ≤12, >12
- Time on DB or OL rimegepant milestone categories:
  - ≥3 months, defined as ≥11 weeks
  - ≥6 months, defined as ≥23 weeks.
- Cumulative DB or OL rimegepant exposure (tablets), derived by summing number of tablets taken per day across records with complete study medication start date and wallet type identifier of DB rimegepant or OL rimegepant.
- Average DB or OL rimegepant exposure (tablets per month), derived as (1) cumulative DB or OL rimegepant exposure (tablets) if time on DB or OL rimegepant <2 weeks, or (2)  $4 \times \text{cumulative DB or OL rimegepant exposure} / \{\text{time on DB or OL rimegepant}\}$  if time on DB or OL rimegepant ≥2 weeks
- Total DB or OL rimegepant exposure (tablets) summed across all subjects, derived by summing cumulative DB exposure across all subjects
- Total DB or OL rimegepant exposure (patient-years), derived by summing  $(\text{DB or OL rimegepant end date} - \text{DB or OL rimegepant start date} + 1) / 365.25$  across all subjects.

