  - All the time. Defined as as-treated treatment group not equal to as-randomized treatment group, i.e., any of the following:
    - Randomized to rimegepant who took (1)  $\geq 1$  tablet from a DB placebo wallet, and (2) no tablets from a DB rimegepant wallet
    - Randomized to placebo who took (1)  $\geq 1$  tablet from a DB rimegepant wallet, and (2) no tablets from a DB placebo wallet.
  - At least once. Defined as any of the following:
    - Randomized to rimegepant who took  $\geq 1$  tablet from a DB placebo wallet
    - Randomized to placebo who took  $\geq 1$  tablet from a DB rimegepant wallet.
- Time on DB study drug >14 weeks.

Results for all categories are displayed, even those with 0 counts.

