### OL Rimegepant Treatment Compliance

The frequency table of OL rimegepant treatment compliance is provided by treatment group for the OL rimegepant safety analysis set, and displays the following categories:

- OL rimegepant tablet count compliance  $\geq 80\%$  from OL rimegepant start to later of last scheduled OLE Phase visit or OL rimegepant end. Tablet count compliance is derived as  $100 \times \text{cumulative exposure} / \text{required exposure}$ , where
  - Cumulative OL rimegepant exposure is defined in Section 6.2.6.1.
  - Required OL rimegepant exposure is derived as  $\text{integer}((n + 1)/2)$ , where  $n = \text{OL maxdate} - \text{OL rimegepant start date} + 1$ .
    - OL maxdate is defined as the latest of the (1) scheduled Week 14 and 24/EOT visit dates, and (2) OL rimegepant end date. Scheduled visits are identified from visit labels, and therefore exclude those containing “unscheduled” in the visit label.
- Average OL rimegepant exposure (tablets per month) categories:
  - >16.8 (> 20% above EOD dosing)
  - >15.4 (> 10% above EOD dosing)
  - $\geq 12.6$  to  $\leq 15.4$  ( $\pm 10\%$  of EOD dosing)
  - $\geq 11.2$  to  $\leq 16.8$  ( $\pm 20\%$  of EOD dosing)
  - $\geq 12.6$  ( $\geq 90\%$  compliant with EOD dosing)
  - $\geq 11.2$  ( $\geq 80\%$  compliant with EOD dosing)

Average OL rimegepant exposure is defined in Section 6.2.6.1.

- OL rimegepant tablets taken per month for 3 consecutive months categories:  $\geq 12$ ,  $\geq 13$ , and  $\geq 14$ 
  - Tablets per month are assessed by the number of 4-week (28-day) intervals in which a subject exceeded select OL rimegepant tablet counts from the OL rimegepant start date to the OL rimegepant end date, where the number of 4-week intervals are consecutive (see Section 6.3.1 for months).
- $>1$  OL rimegepant tablet taken on any 1 day. This is determined from the derived number of OL rimegepant tablets taken per day, which takes overlapping records into account (see Section 9.5).
- Consecutive OL rimegepant dosing days (see Section 9.5)
- Time on OL rimegepant  $>14$  weeks
- OL rimegepant start on or before DB study drug end. Defined as nonmissing OL rimegepant start date  $\leq$  DB study drug end date.
- OL rimegepant taken but DB study drug never taken. Defined as nonmissing OL rimegepant start date and missing DB study drug start date.

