- OL rimegepant end date: latest of complete dosing date from IP Dosing 1 to 4 and Replacement IP Dosing Wallet 1 to 4 CRF records with number of tablets taken per day >0 and valid OL wallet ID
- OL rimegepant last date:
  - Before the LSLV database lock: OL rimegepant end date derived only for subjects with “yes” or “no” response to the phase completion question on the OLE Subject Status CRF
  - LSLV database lock: OL rimegepant end date

This is an analysis period reference date.

- DB or OL rimegepant start date: study drug start date for subjects whose as-treated DB treatment group is rimegepant; OL rimegepant start date for subjects whose as-treated DB treatment group is placebo. This is an analysis period reference date.
- DB or OL rimegepant end date: study drug end date for subjects whose as-treated DB treatment group is rimegepant; OL rimegepant end date for subjects whose as-treated DB treatment group is placebo
- DB or OL rimegepant last dose date: study drug last date for subjects whose as-treated DB treatment group is rimegepant; OL rimegepant last date for subjects whose as-treated DB treatment group is placebo. This is an analysis period reference date.
- OP start date: earliest of the following: screening visit date – 1 day; eDiary efficacy data date. This is an analysis period reference date.
- OP end date:
  - If the study drug start date is nonmissing: study drug start date – 1 day
  - If the study drug start date is missing and the randomization date is nonmissing: randomization date – 1 day
  - If both study drug start date and randomization date are missing: last contact dateThis is an analysis period reference date.
- Last contact date:
  1. Earliest complete death date from the AE CRF, if it exists.
  2. Otherwise, the latest complete date of the following: AE start or end; ECG; eDiary finding; dosing; informed consent; RTSM randomization; laboratory test collection; nonstudy medication start or end; physical exam; physical measurement; procedure; rating scale; questionnaire; vital sign; visit.
  3. If the last contact date is after the most recent raw database creation date, then it is set to the most recent raw database creation date.
- Death date: refer to the Core SAP.

No imputations are performed on these derived dates unless otherwise specified.

Refer to the Core SAP for the definition of complete dates.

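### The combined rimegepant safety set is defined by doses taken but dated from the as-treated label, so placebo-randomized subjects with mixed wallets are left out or enter late

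*SAP*

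**What the plan says.** Protocol 9.2 defines the combined set by dose alone: at least one "dose of double-blind or open-label rimegepant". SAP 4.1 repeats this and adds an operational test: at least one "dose of DB or OL rimegepant, i.e., nonmissing DB or OL rimegepant start date".

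SAP 7.1 has two branches for that date. As-treated rimegepant subjects get their overall study drug start date. As-treated placebo subjects get the "OL rimegepant start date for subjects whose as-treated DB treatment group is placebo". An OL start date needs a dosing record from a valid OL wallet, and derived dates are not imputed unless stated. The end date and last dose date follow the same two branches.

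The label comes from SAP 4.2: if a subject takes at least one "dose of planned randomized study drug, then that subject is considered to have as-treated treatment group equal to as-randomized treatment group". SAP 6.2.6.2 (DB Treatment Compliance) agrees. A placebo-randomized subject counts as having had the wrong drug all the time only after at least one "tablet from a DB rimegepant wallet, and (2) no tablets from a DB placebo wallet". That section also has a separate category for incorrect drug taken at least once.

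Cumulative exposure in SAP 6.2.6.1 follows another rule. It sums tablets on records with "wallet type identifier of DB rimegepant or OL rimegepant", whatever the label. SAP 6.2.6.2 (OL Rimegepant Treatment Compliance) also lists "OL rimegepant taken but DB study drug never taken".

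**The concern.** The dose definition and its stated equivalent in SAP 4.1 disagree for a type of subject that the SAP itself foresees: randomized to placebo, with at least one placebo tablet and at least one DB rimegepant tablet. The as-treated label suits by-arm tables. Here it is reused to date actual rimegepant exposure, which it does not measure.

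The same date or set drives time on rimegepant and patient-years (SAP 6.2.6.1), exposure-adjusted adverse events (6.4.1.5), and exposure-adjusted LFT elevations and time to first elevation (6.4.2.2). In SAP 6.4.6, every narrative criterion except death is restricted to this set.

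The omission may also be informative. Under Protocol 4.1 and 4.3.3, subjects who leave the double-blind phase early cannot enter the OLE. A placebo-randomized subject who stopped because of a non-fatal event on misdispensed rimegepant would have no start date, and would not be picked out for a narrative.

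**Working it through.** The plan gives no figure on this point, so the check applies its rules case by case.

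**Membership.** Take a subject randomized to placebo. The dose rule asks for at least one rimegepant tablet, DB or OL. The date rule asks for a nonmissing start date under SAP 7.1.

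| DB placebo tablets | DB rimegepant tablets | OLE | As-treated | Start date | Dose rule | Date rule |
|---|---|---|---|---|---|---|
| ≥1 | 0 | no | placebo | none | out | out |
| ≥1 | 0 | yes | placebo | first OL dose | in | in |
| ≥1 | ≥1 | no | placebo | none | **in** | **out** |
| ≥1 | ≥1 | yes | placebo | first OL dose | in | in, but late |
| 0 | ≥1 | either | rimegepant | first DB dose | in | in |

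The third row was tested with 1, 8, 16 and 41 DB rimegepant tablets, and the two rules disagreed in all four cases. Rimegepant-randomized subjects showed no membership mismatch. With mixed wallets, however, their time on rimegepant includes placebo days.

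A subject with OL drug but no DB drug meets the dose rule. SAP 4.2 gives no as-treated DB group, so neither branch of SAP 7.1 applies. This is a reading of the text, not one of the tabulated cases.

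**Exposure, illustrative case.** Assumptions:
- One wrong dispensation of 2 wallets of 8 tablets (Protocol 7.2.2) gives 16 rimegepant tablets on Days 1, 3, ..., 31.
- Placebo follows on Days 33, 35, ..., 85.
- OL doses fall on Days 87, 89, ..., 169, which is (169 − 87)/2 + 1 = 42 doses over 83 days, or 83/7 = 11.86 weeks.

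SAP 6.2.6.1 computes average exposure as 4 × cumulative tablets / weeks on drug.
- As the SAP stands: 4 × (16 + 42)/11.86 = **19.6** tablets per month.
- With one misdispensed wallet instead of two: 4 × (8 + 42)/11.86 = 16.9.
- With no mix-up: 4 × 42/11.86 = 14.2.
- First to last rimegepant tablet, with placebo days left in: 169/7 = 24.14 weeks, so 4 × 58/24.14 = 9.6.
- Same span without Days 32 to 86 (55 days): (169 − 55)/7 = 16.29 weeks, so 4 × 58/16.29 = 14.2.

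For scale, the DB and OL compliance tables in SAP 6.2.6.2 use 16.8 tablets per month as the mark for more than 20% above every-other-day dosing. This subject never exceeded that schedule.

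**Split between the two errors.** The Protocol expects about 480 of 600 subjects to enter the OLE. If entry were unrelated to the mix-up, 1 − 480/600 = 20% of affected subjects would be excluded and 80% would enter late.

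**The case against.** The best defence is that few subjects are touched and that nothing is lost to a careful reader. Kits are assigned by number through RTSM (Protocol 7.2.2), so mix-ups should be rare. Sixteen tablets is near the maximum for one error, because a 4-week interval needs about 14 doses. Affected events stay visible: in the enrolled-set AE listing (SAP 6.4.1), the LFT listing (6.4.2), the LFT line plots with dosing days (6.4.2.2), the study drug listing with wallet type (6.2.6.1), and the incorrect-drug deviations (9.1). The estimand tables for the safety objectives name the DBT and OL rimegepant sets. The safety tables that SAP 8.1 lists for the PCD report omit the combined period.

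Most of this stands, and it limits the size of the point. It does not reconcile SAP 4.1 with 7.1. SAP 6.4.1.5 ties two tables on the combined set to other secondary objective 1. SAP 8.1 includes the narrative listing and all study population tables, which cover combined exposure.

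A reader might infer that the as-treated rule in SAP 4.2 is itself wrong, and that any rimegepant tablet should move a subject to the rimegepant column. The documents do not support that. The rule is a usual convention and works the same way in both arms. Relabelling a subject with 1 rimegepant and 41 placebo tablets would be no more accurate, and would collide with the wrong-drug category in SAP 6.2.6.2. It is also not needed to remove the mismatch.

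A simple span from first to last rimegepant tablet can fairly be criticized too: it gives 9.6 in the example because placebo days count as rimegepant time. The fix has to deal with that.

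**Conclusion.** The inconsistency is real and narrow. For placebo-randomized subjects who took both kinds of DB tablet, SAP 7.1 gives either no date or a late one, although SAP 4.1 and Protocol 9.2 place them in the set from their first rimegepant dose. For subjects with OL drug only, it gives none. Placebo-randomized subjects who took only DB rimegepant are handled correctly, and the as-randomized efficacy analyses are untouched.

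The count is not in the documents. If 0 to 1% of 300 placebo subjects were affected, that would be 0 to 3 people. The 19.6 rests on the assumed dosing days. The 14.2 for no mix-up is a reference value: it leaves out the 16 blinded tablets, so it is not this subject's true exposure.

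Two stronger inferences are not supported. One is that rimegepant events would vanish; they remain in the listings and in the placebo column of the on-DBT tables. The other is that the lack of a data monitoring committee makes the matter worse. These are post-lock report sets, and Protocol 8.1.2 requires SAE reporting within 24 hours regardless of set.

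One limit remains. SAP 7.2 sends the safety period definitions to the Core SAP, which was not available. It refers back to Section 7.1 for the dates, so a correction there seems unlikely but cannot be ruled out.

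**What to change.** In SAP 7.1, derive the DB or OL rimegepant start, end and last dates for every subject from the earliest and latest complete dosing dates with more than 0 tablets from a valid DB rimegepant or OL rimegepant wallet, whatever the as-treated group. Keep the existing database-lock conditions for the last date. Both halves of the SAP 4.1 definition then agree in every case tested, and the OL-only subject gets a date.

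Flag mixed-wallet subjects. In SAP 6.2.6.1, 6.4.1.5 and 6.4.2.2, exclude intervening placebo-wallet days from time on rimegepant and from exposure-adjusted denominators, and apply the same windows to event counts so that numerator and denominator agree. Leave SAP 4.2 unchanged for the by-arm on-DBT tables.

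No new data are needed: SAP 6.2.6.1 already merges wallet type onto the dosing records. The cost is one revised set of definitions and a small programming change. A few subjects at most would enter the combined set or change their start date.

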## 7.2 Analysis Periods

Measurements are slotted into analysis periods based on comparing measurement dates to analysis period reference dates (time is not applicable).

Analysis periods are defined according to endpoints as follows:

- eDiary efficacy endpoints (migraine days, acute migraine-specific medication days, acute migraine medication days, headache days)

- OP: eDiary efficacy data date on or after the OP start date through the OP end date. Note that this is a subset of the pretreatment analysis period.
- 28-day OP: eDiary efficacy data date on or after the OP start date through the earlier of {OP start date + 27 days; OP end date}. Note that this is a subset of the OP analysis period, and is used only to assess baseline characteristics and relevant protocol deviations.
- On-DBT efficacy:
  - If the DB study drug last date or OL rimegepant start date is not missing: eDiary efficacy data date on or after the DB study drug start date through the earlier of {DB study drug last date + 1 day; OL rimegepant start date – 1 day}
  - If the DB study drug last date and OL rimegepant start date are both missing: eDiary efficacy data date on or after the DB study drug start date + 1 day

This period is used to assess efficacy during the DBT Phase.

- Pretreatment characteristics and safety endpoints \*
  - Pretreatment: This period is used to derive baseline values.
  - On-DBT safety: This period is used to assess safety endpoints on DBT for the DBT safety analysis set.
  - Post-DBT pre-OL rimegepant safety: This period is used to assess safety endpoints during the interim period (i.e., post-DBT pre-OL rimegepant) for the interim safety analysis set.
  - On-OL rimegepant safety: This period is used to assess safety endpoints on OL rimegepant for the OL rimegepant safety analysis set.
  - On-DB or OL rimegepant safety: This period is used to assess safety endpoints on DB or OL rimegepant for the DB or OL rimegepant safety analysis set.
  - On-treatment safety: This period is used to derive analysis visit windows for slotting measurements, and may also be used to assess blinded safety endpoints on treatment in an integrated safety report, as needed.
  - Follow-up safety: This period is used to assess safety endpoints during follow-up for the follow-up safety analysis set.
- Outcomes research endpoints (MSQ, MIBS, MFIQ, HIT-6, WPAI – Migraine, PGA – Migraine) \*
  - DBT outcomes research: This period is used to assess outcomes research endpoints during the DBT Phase for the DBT efficacy analysis set.
  - OL rimegepant outcomes research: This period is used to assess outcomes research endpoints during the OLE Phase for the DBT efficacy analysis set.

For endpoints marked with “\*”, refer to the Core SAP for the definitions of analysis periods in Phase 2/3/4 multiple-dose studies with both DBT and OLE Phases. See Section 7.1 for derived dates for determining analysis periods.

### 7.3 Analysis Visit Windows

Refer to C4951012 Protocol Section 4.3 for the schedule of assessments.

Refer to the Core SAP for defining randomization days, study days, rimegepant study days, and follow-up days in Phase 2/3/4 multiple-dose studies with both DBT and OLE Phases.

General analysis visit windows are shown in [Table 6](#). MFIQ DBT analysis visit windows are shown in [Table 7](#).

**Table 6 General Analysis Visit Windows**

Analysis Period Analysis Visit	Abbreviation in Listings	Analysis Day Analysis Visit Window	Target Day
Pretreatment	PRETRT	Randomization Day	
Screening *		$\leq -7$	
Pre-randomization *	Prerand	-6 to -1	
Baseline *		1	
Post-randomization @	Postrand	$\geq 2$	
Outcomes Research/On-Treatment Safety	On-Treatment Safety: ONTRT	Study Day	
Week 2		2 to 21	14
Week 4		22 to 42	28
Week 8		43 to 70	56
Week 12		71 to 91	84
Week 14		92 to 112	98
Week 24		155 to 182	168
Extension @		$\geq 183$	
Follow-Up Safety	FU	Follow-Up Day	
Follow-Up Week 2	FU Week 2	8 to 28	14
Follow-Up Extension @	FU Ext	$\geq 29$	

\* For subjects in the enrolled analysis set excluded from the full analysis set, the visit label is used for slotting.

@ Denotes an extended visit in the analysis period and is displayed only in listings

